9.1.1. Relationship to Study Drug

Adverse events will be classified as “related” to study treatment if the relationship was rated by the investigator as possibly related or probably related. Adverse events related to any study drug (relugolix or placebo and E2/NETA or placebo) will be considered as related to study drug.

9.1.2. Severity of Adverse Event

Grade 2 or above adverse events will be summarized by SOC, PT, and/or maximum severity, relationship to study treatment.

9.1.3. Serious Adverse Event

Serious adverse events will be summarized by SOC, PT, and/or maximum severity, relationship to study treatment.

The data handling conventions for and the definition of a serious adverse event are discussed in this section. All deaths during the study, including the post treatment follow-up period, and deaths that resulted from a process that began during the study, should be included in the

analysis. For more details, deaths occurring during the following time periods or under the following conditions should be considered:

- Deaths occurring during participation in any study, or during any other period of drug exposure
- Deaths occurring after a patient leaves a study, or otherwise discontinues study drug, whether or not the patient completes the study to the nominal endpoint, if the death:
 - Is the result of a process initiated during the study or other drug exposure, regardless of when it actually occurs; or
 - Occurs within a time period that might reflect drug toxicity for a patient leaving a study or otherwise discontinuing drug. For drugs with prompt action and relatively short elimination half-lives, 4 weeks is a reasonable time period. For drugs with particularly long elimination half-lives or drug classes with recognized potential to cause late occurring effects, deaths occurring at longer times after drug discontinuation should be evaluated.

9.1.4. Adverse Event Leading to Withdrawal of Study Drug

Adverse events leading to withdrawal of study drug are those adverse events collected from the adverse event CRF pages with “drug withdrawn” as the action taken with study drug.

Adverse events with “drug withdrawn” as action taken due to any one of the components of study drug will be considered as leading to withdrawal of study drug.

9.1.5. Adverse Events Leading to Dose Interruption

Adverse events leading to dose interruption are those adverse events collected from the adverse event CRF pages with “drug interrupted” as their action taken with study drug.

Adverse events with “drug interrupted” as action taken due to any one of the components of study drug will be considered as leading to dose interruption.

9.1.6. Adverse Events Resulting to Fatal Outcome

Adverse events resulting in a fatal outcome are those adverse events collected from the adverse event pages with “fatal” as their outcome.

The fatal events, if any, will be provided in a by-subject listing.

9.1.7. Adverse Event Categories

In addition, adverse event categories defined in [Table 12](#) will be summarized by decreasing frequency of PT under each safety population. Incidence of vasomotor symptoms by 12 weeks will be compared between relugolix Group A and relugolix Group B. Comparative statistics (such as p-values, 95% CIs, risk ratio) will be provided. Vasomotor symptoms throughout the studies will be summarized by SOC, PT, and maximum severity.

Table 12: Constitution of Adverse Event Categories

Category	Search Criteria
Bone health events	Osteoporosis/Osteopenia SMQ (broad) Fracture (custom SMQ): All preferred terms including the term “fracture,” excluding “Tooth fracture” and “Fracture of penis”
Hepatic disorders	Drug-related hepatic disorders – comprehensive SMQ (narrow)
Metabolic disorders	Dyslipidemia SMQ (broad) Hyperglycemia/new onset diabetes mellitus SMQ (narrow)
Vasomotor symptoms	The following 5 preferred terms will be included: Hyperhidrosis; Feeling hot; Hot flush; Night sweats; Flushing
Mood disorders	MedDRA Depression and Suicide/Self-Injury SMQ (broad)

Abbreviations: HLT, High-Level Term; MedDRA, Medical Dictionary for Regulatory Activities; SMQ, Standardised MedDRA Query.

9.2. Laboratory Data

Laboratory parameters, including chemistry and hematology panels, specified as per protocol, and collected from the central laboratory will be tabulated and presented in by-patient listings. Urinalysis and hepatitis virus serological test results will be provided in by-patient listing only.

The National Cancer Institute CTCAE Grading Scale with numeric component will be used to categorize toxicity grade for laboratory parameters (CTCAE v5.0, dated 17 Nov 2017). Parameters that have criteria available for both low and high values (eg, hypercalcemia for a high value of calcium and hypocalcemia for a low value of calcium) will be summarized for both criteria (low and high). Patients will only be counted once for each criterion. The same patient can be counted for both criteria if she has laboratory values meeting each criterion. Shift tables will be provided for each gradable parameter to summarize Baseline toxicity grade versus worst post-Baseline toxicity grade. For laboratory parameters that are not gradable by the CTCAE, a shift table based upon the normal range (low, normal, and high) will be provided for each parameter to summarize the Baseline versus worst post-Baseline results.

Boxplots of laboratory values over time will be plotted for key laboratory parameters. These laboratory parameters include, but are not limited to, hematology (hemoglobin, platelets,

Statistical Analysis Plan
Amendment 1: Effective June 14, 2019

MVT-601-3001 and 3002

leukocytes, neutrophils), creatinine, glomerular filtration rate, and hepatic function panel (alanine aminotransferase [ALT], aspartate aminotransferase [AST], alkaline phosphatase [ALP], and total bilirubin).

The change from Baseline to each post-Baseline study visit will be presented by treatment group for each laboratory test in both tables and figures.

The number and proportion of patients with liver test elevations will be presented by treatment group. Liver test elevations are assessed by using post-Baseline results for ALT, AST, ALP, and total bilirubin based on the definitions presented in [Table 13](#).

Table 13: Categories of Liver Test Elevations

Laboratory Test	Category
ALT or AST	ALT or AST > ULN - < 3xULN ALT or AST ≥ 3x to < 5x ULN ALT or AST ≥ 5x to < 8x ULN ALT or AST ≥ 8x to < 10x ULN ALT or AST ≥ 10 to < 20x ULN ALT or AST ≥ 20x ULN
Total bilirubin	Total bilirubin > 2 × ULN
ALT or AST and total bilirubin	ALT or AST ≥ 3 × ULN + total bilirubin > 2 × ULN
ALT or AST, total bilirubin, and ALP	ALT or AST ≥ 3 × ULN + total bilirubin > 2 × ULN + ALP < 2 × ULN

Abbreviations: ALP, alkaline phosphatase; ALT, alanine aminotransferase; AST, aspartate aminotransferase; ULN, upper limit of normal.

The number and percentage of patients with concurrent (defined as measurements on the same day) ALT or AST ≥ 3 times ULN and total bilirubin > 2 times ULN will also be presented.

9.3. Other Safety Analyses

9.3.1. Electrocardiograms

ECG interval results and changes from Baseline will be summarized descriptively for each scheduled visit in both tables and figures using data provided by and read by central reading.

A categorical analysis of corrected QT interval using Fridericia's calculation (QTcF) intervals will also be performed for each scheduled visit and for the maximum post-Baseline value. The number and percentage of patients in each QTcF interval category (< 450 msec, 450 to 480 msec, 481 to 500 msec, and > 500 msec) will be summarized. Categories of changes from Baseline (≥ 30 msec and ≥ 60 msec) will be summarized as well.

ECG intervals will be presented in by-patient listing. Overall ECG assessments performed by local reading will also be listed.

9.3.2. Visual Acuity

Visual Acuity Score at Baseline and at each scheduled post-Baseline assessment time point will be presented in a by-patient listing.

9.3.3. Vital Signs

Blood pressure (systolic and diastolic), heart rate, and BMI will be summarized at Baseline and each subsequent scheduled assessment by treatment group. Change from Baseline will be calculated and presented for each parameter at all scheduled post-Baseline assessment time points in both tables and figures. All vital sign data will also be provided in by-patient listings.

Potentially clinically significant abnormalities in vital signs are defined in [Table 14](#), and they will be summarized by using post-Baseline values that meet the defined criteria. Potentially clinically significant abnormalities will also be flagged in by-patient listings.

Table 14: Categories of Potentially Clinically Significant Abnormalities in Vital Signs

Parameter	Category
Systolic blood pressure	≥ 140 mmHg
	≥ 180 mmHg
	≤ 90 mmHg
	Increase of ≥ 20 mmHg from Baseline Decrease of ≥ 20 mmHg from Baseline
Diastolic blood pressure	≥ 90 mmHg
	≥ 105 mmHg
	≤ 50 mmHg
	Increase of ≥ 15 mmHg from Baseline Decrease of ≥ 15 mmHg from Baseline
Heart rate	≥ 120 bpm
	< 45 bpm
	Increase of ≥ 15 bpm from Baseline Decrease of ≥ 15 bpm from Baseline

Abbreviations: bpm, beats per minute; mmHg, millimeters of mercury.

9.3.4. Endometrial Biopsy

Primary diagnosis of endometrial biopsy assessment will be summarized at Baseline and at scheduled assessment by treatment group. All endometrial biopsy data will also be provided in a by-patient listing.

Primary diagnosis from pathologist evaluation will be categorized by medical monitor's review in [Table 15](#) and will be summarized using frequencies and percentages, summarized for each treatment group. All endometrial biopsy data will also be provided in by-patient listings.

Table 15: Categories of Primary Diagnosis in Endometrial Biopsies

Normal-Proliferative	
 Weakly proliferative Proliferative Disordered proliferative
Normal-Secretory/Menstrual/Mixed	
 Secretory Menstrual Progestational/Decidulized/Mixed
Normal-Atrophic or Minimally Stimulated	
 Atrophic Indeterminate/Inactive
Hyperplasia	
 Simple hyperplasia without atypia Simple hyperplasia with atypia Complex hyperplasia without atypia Complex hyperplasia with atypia
Carcinoma	—
Inadequate	—
Missing	—
Additional Diagnosis (Other reported finding)	
 Reactive/Inflammatory Polyp Metaplasia Glandular and/or Stromal Breakdown

9.3.5. Bone Mineral Density

Corrected BMD data will be used for analysis as determined by the central radiology laboratory in the 3 prespecified anatomical locations: lumbar spine (L1–L4), total hip, and femoral neck.

BMD at Baseline, Week 12 and Week 24 visits will be summarized descriptively by treatment group and each anatomical location. Percentage changes from Baseline along with 95% CIs of mean percentage changes will be also summarized by treatment group and anatomical location. Mean percentage change from Baseline with its corresponding 95% CI will be plotted by visit, treatment group, and anatomical location.

To support the inclusion of E2/NETA in the treatment regimen, the safety endpoint of mean percent change from Baseline in BMD at the lumbar spine at Week 12 will be analyzed using pooled data from the two replicate studies (MVT-601-3001 and MVT-601-3002) with a formal

Statistical Analysis Plan
Amendment 1: Effective June 14, 2019

MVT-601-3001 and 3002

comparison of the relugolix + E2/NETA group (Group A) versus the relugolix + delayed E2/NETA group (Group B) (details in the Integrated Summary of Safety Statistical Analysis Plan).

In addition, the difference of percentage change from Baseline between treatment groups (relugolix + E2/NETA group versus the relugolix + delayed E2/NETA group at 12 weeks, relugolix + E2/NETA versus placebo group at 12 and 24 weeks, and relugolix + delayed E2/NETA group versus placebo group at 12 weeks) will be summarized at each visit by anatomical location along with the corresponding 95% CIs.

To account for participants whose BMD assessment may have been obtained outside of the protocol-specified window (Week 12 \pm 3 weeks, Week 24 \pm 3 and 4 weeks), a sensitivity analysis by visit will be conducted that includes all women who underwent DXA at both time points, regardless of whether the image was procured during the prespecified time window.

A mixed-effects model with repeated measures will be used to describe treatment effect on BMD at 12 and 24 weeks. The model will have treatment group, age at Baseline, visit, Baseline BMD value, stratification factors (geographic region and menstrual blood loss volume), race (African American versus Other), and BMI at Baseline as fixed effects using an unstructured variance-covariance matrix. Least square means on each anatomical location will be presented and plotted at each visit with associated 95% CIs. Categorical representation of percentage change from Baseline to 12 and 24 weeks of treatment will be presented by the number and proportion of patients who had BMD declines of $\leq 2\%$, $> 2\%$ to 3% , $> 3\%$ to 5% , $> 5\%$ to 8% , and $> 8\%$ by treatment group and anatomical location. The 95% CIs will be provided for the respective proportions.

Categorical changes from Baseline in overall BMD (defined as lumbar spine and total hip) also will be assessed at 12 and 24 weeks. Femoral neck evaluates a smaller area of bone mass than the total hip and is prone to lower precision in the measurement ([ISCD Official Positions, 2015](#); [Leslie, 2007](#)). Since femoral neck BMD may be associated with discordant readings compared with the total hip or lumbar spine due to technical considerations, it will not add meaningful interpretation of overall BMD changes in response to treatment.

Z-scores will be summarized by treatment group, visit, and anatomical location with descriptive statistics including 95% CIs, and the number and percentage of patients with a Z-score < -2.0 will be presented by treatment group, visit, and anatomical location.

BMD percentage changes from Baseline will also be summarized by intrinsic factors (eg, age, race, body mass index) and extrinsic factors (eg, geographic region).

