To determine the safety of 24 weeks of relugolix 40 mg once daily co-administered with either 12 or 24 weeks of E2 1 mg and NETA 0.5 mg in women with heavy menstrual bleeding associated with uterine fibroids compared with placebo for 24 weeks	Treatment-emergent adverse events, change in vital signs (including weight), clinical laboratory tests, and electrocardiograms
To determine the percent change from Baseline to Week 12 in bone mineral density at the lumbar spine (L1-L4) in the relugolix + E2/NETA group compared with the relugolix + delayed E2/NETA group in women with heavy menstrual bleeding associated with uterine fibroids	Percent change from Baseline to Week 12 in bone mineral density at the lumbar spine (L1-L4) in the relugolix + E2/NETA group compared with relugolix + delayed E2/NETA group as assessed by DXA

Objective(s)	Endpoint(s)
To determine the change in bone mineral density of women with heavy menstrual bleeding associated with uterine fibroids treated with 24 weeks of relugolix 40 mg once daily co-administered with either 12 or 24 weeks of E2 1 mg and NETA 0.5 mg compared with placebo for 24 weeks	Percent change from Baseline to Week 24 in bone mineral density at the lumbar spine (L1-L4), total hip, and femoral neck as assessed by DXA
To determine the incidence of vasomotor symptoms with relugolix 40 mg once daily co-administered with either 12 or 24 weeks of E2 1 mg and NETA 0.5 mg in women with heavy menstrual bleeding associated with uterine fibroids	Incidence of vasomotor symptoms
Pharmacokinetic and Pharmacodynamic	
To evaluate the pharmacokinetic and pharmacodynamic effects of 24 weeks of relugolix 40 mg once daily when co-administered with either 12 or 24 weeks of E2 1 mg and NETA 0.5 mg	
 • Predose trough concentrations (C_{τ}) of relugolix, and NET and Baseline-adjusted E2 concentration • Absolute and changes from Baseline to Week 24 in predose concentrations of LH, FSH, E2, and progesterone
Exploratory	
To determine the benefit of 24 weeks of relugolix 40 mg once daily co-administered with either 12 or 24 weeks of E2 1 mg and NETA 0.5 mg compared with placebo on patient-reported quality of life outcome measures (EQ-5D-5L)	Change from Baseline to Week 24 in the EQ-5D-5L Scale score

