Change from Baseline to Week 24 in the UFS-QoL Symptom Severity Scale score	mITT	Mixed-effects model	P < 0.05	Week 12, 24	LS means for change
Change from Baseline to Week 24 in the UFS-HRQL total score	mITT	Mixed-effects model	P < 0.05	Week 12, 24	LS means for change
Change in PGA for uterine fibroid related function from Baseline to Week 24	mITT	Mixed-effects model	P < 0.05	Monthly	LS means for absolute and change
Change in PGA for uterine fibroid symptoms from Baseline to Week 24	mITT	Mixed-effects model	P < 0.05	Monthly	LS means for absolute and change
Proportion of patients achieving improvement in PGA for uterine fibroid symptoms from Baseline to Week 24	mITT	Cochran-Mantel-Haenszel test	P < 0.05	Monthly	Frequency and percentages
Proportion of patients achieving improvement in PGA for uterine fibroid related function from Baseline to Week 24	mITT	Cochran-Mantel-Haenszel test	P < 0.05	Monthly	Frequency and percentages
Safety Related Endpoints					
% Change from Baseline to Week 12 in BMD (pooled data)	Safety population	Mixed-effects model Relugolix Group A vs B	P < 0.05	Week 12	LS means Diff (95%CI)

Secondary Endpoints	Analysis Population	Statistical Method/Test	Declare Statistical Significance ^a	Time Points of Summary	Summary Statistics
% Change from Baseline in BMD	Safety population	Mixed-effects model Relugolix Group A vs Placebo at 12/24 weeks; Relugolix Group B vs Placebo at 12 weeks		Week 12, 24	LS means Diff (95%CI)
Exploratory Secondary Efficacy Endpoints					
Change from Baseline to Week 24 in the Menorrhagia Impact Questionnaire Score for physical activities	mITT	Descriptive		Monthly	Frequency and percentages
Change from Baseline to Week 24 in the Menorrhagia Impact Questionnaire Score for social and leisure activities	mITT	Descriptive		Monthly	Frequency and percentages

Abbreviations: KM, Kaplan-Meier; LS, least squares; mITT, modified intent-to-treat; NRS, Numerical Rating Scale; Q, question; UFS-HRQL, Uterine Fibroid Scale – Health-related Quality of Life.

^a P-values are two-sided.

APPENDIX 2. DERIVATION AND PSYCHOMETRIC EVALUATION OF A UFS-QOL BLEEDING AND PELVIC DISCOMFORT SCALE

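### The Week 24 BMD objective compares both relugolix regimens with placebo, but no between-group difference with CI is planned for the delayed E2/NETA group versus placebo at Week 24

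*SAP*

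**What the plan says.** Table 1 (SAP Section 1.1, Safety) has an objective on BMD change after 24 weeks of relugolix, "co-administered with either 12 or 24 weeks of E2 1 mg and NETA 0.5 mg compared with placebo for 24 weeks". The matching endpoint is "Percent change from Baseline to Week 24 in bone mineral density at the lumbar spine (L1-L4), total hip, and femoral neck as assessed by DXA".

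Section 9.3.5 lists the between-group differences in percent change to be summarized with 95% CIs at each site:
- Group A versus Group B at 12 weeks;
- "relugolix + E2/NETA versus placebo group at 12 and 24 weeks";
- "relugolix + delayed E2/NETA group versus placebo group at 12 weeks".

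Appendix 1, in the row for percent change in BMD, gives the mixed-model contrasts as "Relugolix Group A vs Placebo at 12/24 weeks; Relugolix Group B vs Placebo at 12 weeks". The same restriction appears in both SAP versions in the file (Amendment 1 and the version without that label). Neither gives a reason.

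Section 9.3.5 also plans results for each arm, covering all three groups at Weeks 12 and 24: mean percent change with 95% CI, least squares means by visit with 95% CIs, categories of BMD decline with 95% CIs, and Z-scores.

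**The concern.** The objective is a comparison with placebo and names both regimens. By Section 2.1, Group B takes relugolix alone for 12 weeks and then relugolix with E2/NETA for 12 weeks. The Week 12 contrast with placebo therefore describes only the first phase. Table 3 gives two on-treatment BMD windows, Weeks 12 and 24, so Week 24 is the only planned on-treatment point that can show whether an early difference from placebo persists, grows or shrinks once E2/NETA is added.

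The later DXA scans described in Section 3.3 do not fill the gap. They are limited to women who do not enter the extension and who lost more than 2% at the spine or hip, which is a selected subset.

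As written, the study report would give a placebo-referenced Week 24 result for one regimen and not the other. A contrast added after unblinding would be post hoc.

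**Working it through.** **1. Objective against planned contrasts**

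| Contrast with placebo | Named in the Week 24 objective | Planned in 9.3.5 | Planned in Appendix 1 |
|---|---|---|---|
| Group A, Week 12 | no | yes | yes |
| Group A, Week 24 | yes | yes | yes |
| Group B, Week 12 | no | yes | yes |
| Group B, Week 24 | yes | **no** | **no** |

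One of the two Week 24 contrasts in the objective is missing, at all three sites.

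**2. Can the planned mixed model supply it?** Section 9.3.5 lists the fixed effects as treatment, age, visit, baseline BMD, the stratification factors, race and BMI. There is no treatment-by-visit term, whereas Sections 7.4.1 and 7.4.2 include one explicitly for the efficacy models. With additive effects, for a woman with covariates x,

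mean(group g, visit v) = μ + treatment_g + visit_v + covariates(x)

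so

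mean(B, v) − mean(placebo, v) = treatment_B − treatment_placebo,

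which does not depend on v. The fitted Group B minus placebo difference is the same number at Weeks 12 and 24. The same holds for Group A versus placebo, although Appendix 1 asks for that contrast at both visits. The Week 24 least squares means from this model cannot stand in for the missing contrast, and adding Week 24 to the Appendix 1 line alone would not repair it.

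**3. The SAP's own BMD figure.** Section 2.2.2 plans 260 per group (pooled, A versus B, lumbar spine, Week 12), a difference of 1.25 points, SD 4% and up to 15% dropout, for at least 90% power at two-sided 0.05.

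- Evaluable n = 260 × 0.85 = 221 per group
- SE = 4 × √(2/221) = 0.381
- 1.25 / 0.381 = 3.285; power = Φ(3.285 − 1.96) = 90.7%

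The stated figure reproduces. It is not in dispute, and the point here does not depend on it.

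**4. Illustrative precision of the missing contrast, per study.** Group B and placebo have 130 women each (Section 2.2.1). The SAP gives no SD for Week 24, total hip or femoral neck, so the Week 12 lumbar spine SD of 4% is carried over as an assumption. Dropout is taken as 15% (the BMD assumption) or 20% (the assumption for the primary endpoint).

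Half-width = 1.96 × SD × √(2/n)

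- 15%: n = 130 × 0.85 = 110.5; 1.96 × 4 × √(2/110.5) = 1.05 points
- 20%: n = 130 × 0.80 = 104; 1.96 × 4 × √(2/104) = 1.09 points
- SD 3%, n = 110.5: 0.79; SD 5%, n = 104: 1.36. The range is about 0.8 to 1.4 points.

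**5. What that precision does not deliver.** For a true difference of 1.25 points, SE = 4 × √(2/110.5) = 0.538 and 1.25 / 0.538 = 2.32. Power per study is Φ(2.32 − 1.96), about 64%.

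**The case against.** **Week 24 results are already planned for both arms.** This is true. A reader might infer that this half of the objective goes without any estimate, and Section 9.3.5 does not support that. Both arms get mean changes with CIs, least squares means and decline categories. An unadjusted difference and an approximate CI could be worked out from the two arm means and their intervals. What remains is that the SAP commits to no such difference, adjusted or unadjusted, and two separate intervals are not an interval for the difference.

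**The restriction may be deliberate.** It appears consistently in two sections and two versions. The endpoint cell for this objective names no contrast, while the Week 12 row names A versus B. Section 7.2 also limits comparisons of Group B with placebo to the primary endpoint. But that limit stands in a passage on efficacy endpoints, and Section 9.3.5 itself plans Group B versus placebo for BMD at Week 12. If the omission is intended, the objective is worded too widely and the SAP should say why.

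**The integrated safety plan may cover it.** This SAP assigns to that plan the pooled Week 12 comparison of A with B. The plan is not shown, so whether it also holds a Week 24 Group B contrast is unknown. It would in any case be a pooled result, whereas the objective is stated for each study.

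**The precision figures are borrowed.** This is accepted. They come from Week 12 at the lumbar spine, and Section 9.3.5 itself says the femoral neck is measured less precisely. A reader might also take a half-width near 1.05 to mean that one study could reliably show a 1.25-point difference. At about 64% power it could not.

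**Conclusion.** The mismatch holds, in a narrow form. Table 1 names Group B versus placebo at Week 24, and neither Section 9.3.5 nor Appendix 1 plans that difference or its CI at any of the three sites. Results for each arm are planned, so the safety data on Group B would not be lost. The analysis would be descriptive and outside the gated testing, so neither type I error nor the efficacy conclusions are touched.

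The comparison of objective with contrasts rests on wording alone. The remark on the mixed model assumes that the listed fixed effects are complete. The half-widths of 1.05 and 1.09 points assume that the Week 12 lumbar spine SD of 4% holds at Week 24. They show that the contrast would be informative as an interval estimate, not that each study is powered for it.

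**What to change.** 1. In Section 9.3.5 and in the BMD row of Appendix 1, extend the Group B versus placebo comparison from Week 12 to Weeks 12 and 24. Report the difference and 95% CI at lumbar spine, total hip and femoral neck, labelled as descriptive and outside the gated procedure.
2. Add a treatment-by-visit interaction to the fixed effects of the BMD mixed model in Section 9.3.5, so that each visit has its own difference. With three groups and two visits this uses (3 − 1) × (2 − 1) = 2 degrees of freedom. It also frees the Group A contrasts at Weeks 12 and 24 from being equal.
3. If leaving out the Week 24 contrast was intended, narrow the Table 1 objective instead and state the reason. The interaction is still needed for Group A.

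The cost is two wording changes, one model term and one further contrast per site. The DXA data are already collected under the plan, and no change in sample size or alpha is needed. The change should be made before unblinding.
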